## **3.2 Secondary Purpose**

### 3.2.1 Construct a Predictive Model to Predict the Risk of Adverse Prognosis in Patients With DKD.

- (1) **Study subjects:** patients with diabetic nephropathy.
- (2) **Exposure factors:** glycemic variability index, clinical indicators, intestinal flora, serum metabolites, inflammatory factors.
- (3) **study OUTCOMES:**
  - (1) **Primary end point:** death from any cause, including death from all causes.
  - (2) **Secondary end point:** Unintentional major cardiovascular events (MACE): major cardiovascular events including myocardial infarction, stroke, and unstable angina pectoris.
- (4) **Specific objectives:** Construct a prediction model by incorporating the above indicators to predict the prognosis of DKD patients.

### 3.2.2 Characteristics of Gut Microbiota and Serum Metabolites in Different GV Groups and Their Correlation With Prognosis

- (1) **Study subjects:** patients with diabetic nephropathy
- (2) **Exposure factors:** different glycemic variability (GV) groups.
- (3) **Study outcome:** characteristics of intestinal microbiota and serum metabolites.
- (4) **Specific objectives:** Through 16S rRNA high-throughput sequencing technology and serum non-target liquid chromatography -Mass Spectrometry (LC-MS) was used to investigate the characteristics of intestinal microflora and serum metabolites in patients with different glycemic variability (GV) groups. The relationship between the bacterial co-abundance groups (CAG) and the functional modules of serum metabolites was further established to explore their correlations with glycemic variability and poor prognosis.

## 4. Research Content and Innovation

### 4.1. Research Content

This prospective observational cohort study was designed to investigate the relationship between gut microbiota, serum metabolites, and glycemic variability (GV) and their effect on the prognosis of patients with diabetic nephropathy (DKD).

#### 4.1.1 Assessing the impact of glycemic variability on prognosis in patients with diabetic kidney disease

- (1) in prospective cohort studies, patients with DKD were enrolled, and their blood glucose was monitored with a continuous glucose monitor for 14 days, followed by longitudinal follow @-@ up to record adverse prognostic events.
- (2) The relationship between glycemic variability and prognosis was analyzed, and the optimal TIR control target for DKD patients was discussed.

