Reducing the incidence of hypoglycemia and minimizing blood glucose fluctuations are crucial for improving the prognosis of diabetic kidney disease (DKD) patients. Timely and accurate blood glucose monitoring is essential for maintaining good glycemic control. However, self-monitoring of blood glucose (SMBG) faces limitations such as poor adherence and constraints from environmental and time factors. Continuous glucose monitoring systems (CGMS) provide diabetic patients with multiple reliable glucose assessment metrics. These include time in range (TIR) and its derivatives time above range (TAR) and time below range (TBR) for evaluating target-range compliance, daily glucose fluctuations measured by standard deviation (SD), coefficient of variability (CV), and mean amplitude of glycemic excursions (MAGE), as well as daily mean absolute differences (MODD) to monitor intra-day variability. Additionally, the system assesses hyperglycemic index (HBGI) and hypoglycemic index (LBGI) to identify risks of hyperglycemia and hypoglycemia [18]. In 2019, the Advanced Technology and Therapy for Diabetes Committee (ATT) emphasized in the "International Expert Consensus on Clinical Application of Continuous Glucose Monitoring" that the core monitoring indicator TIR combined with different blood glucose monitoring indicators can serve as a baseline for evaluating glycemic control. In the 2020 China guidelines for the prevention and treatment of type 2 diabetes, TIR was also included in the control targets [19]. Beck et al. [20] used SMBG data from patients in the Diabetes Control and Complications Trial (DCCT) to calculate TIR and found that TIR was independently associated with the progression of diabetic retinopathy (DR) and proteinuria, suggesting that TIR could serve as an effective end-point indicator in clinical trials. Lu et al. evaluated the relationship between HbA 1C estimated from CGM mean glucose and TIR in 2,893 patients with type 2 diabetes, observing a good linear relationship between the two( $r=-0.91$ ,  $P<0.001$ ). This parameter is more reliable than HbA1c data and can be applied to patients with advanced chronic kidney disease (CKD), including those undergoing dialysis. **Currently, few studies have analyzed the relationship between CGM-derived indicators and the risk of adverse renal outcomes in patients with diabetic kidney disease (DKD).**

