#### **2.1.4 Hypothesis and Significance of the Research**

To date, no studies have explored the impact of gut microbiota on the prognosis of diabetic kidney disease (DKD) patients with varying degrees of glycemic variability. Based on existing literature, we propose the following hypotheses: 1) Glycemic variability and specific gut microbiota serum metabolites serve as predictors of adverse cardiovascular events in DKD patients; 2) The gut microbiota and serum metabolites of DKD patients are associated with glycemic variability (GV), which may influence patient outcomes through gut microbiota metabolism. Our proposed methodology includes: 1) Assessing glycemic variability in DKD patients via continuous glucose monitoring (CGM) to investigate its relationship with prognosis and determine optimal glycemic variability control targets. 2) Utilizing 16S rRNA high-throughput sequencing and serum non-targeted liquid chromatography-mass spectrometry (LC-MS) to analyze the relationship between gut microbiota, metabolites, inflammatory factors, and DKD patient prognosis. This study aims to optimize clinical management strategies, establish risk prediction models, promote interdisciplinary research, and improve patient quality of life. The findings will provide new scientific evidence and tools for precision treatment and prognosis management in DKD patients, demonstrating significant scientific and clinical value.

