**(3) Study endpoint:**

**① Primary end point:** progression of DKD. Progression of DKD was defined as renal failure (requiring transplantation or dialysis, or persistent eGFR <15 ml/min/1.73 m^2) or a persistent decline of 30% in eGFR from baseline.

**② Secondary End Points:** I. Cardiogenic Death: Death caused by cardiac disease or related complications. II. Major Adverse Cardiovascular Events (MACE): Including myocardial infarction, stroke, unstable angina pectoris, and other significant cardiovascular events. III. Kidney Transplantation: Successful cases of kidney transplantation surgery. IV. Hypoglycemic Events: Documentation of the frequency and severity of hypoglycemia occurrences.

**(4) Specific objectives:** I. Evaluate the relationship between GV and prognosis in patients with DKD and determine the optimal GV control target. II. Screen for biomarkers of gut microbiota, metabolites, and inflammatory factors associated with DKD prognosis.

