#### **5.6 Experimental Scheme**

Step	Period	Filter period	Period of wearing CGM			Follow-up period		
	Study follow-up	Visit 0	Visit 1	Visit 2	Visit 3	Visit 4	Visit 5	Visit 6
	Study date (days)	1 day before enrollment	1 day after enrollment	7 days after enrollment	14 days after enrollment	Within 1 year after enrollment	Within 2 years after enrollment	Within 3 years after enrollment

1	Selection and exclusion criteria	✓						
2	Sign the informed consent form.	✓						
3	Adorn CGM		✓					
4 clinical data	Basic information of the subjects		✓					
	Clinical diagnosis		✓					
	Personal history		✓					
	History of past illness		✓					
	Check-up		✓					
5 clinical examination Inspection	Routine blood test			✓				
	Liver function			✓				
	Renal function			✓				
	HbA1c			✓				
	Blood fat			✓				
	Fasting insulin (FIns)			✓				
	Blood sugar			✓				
	Thyroid function			✓				
	Coagulation function			✓				
6	Medication during CGM monitoring				✓			
7	Fecal collection		✓					
8	Blood collection		✓					
9	Medications taken after discharge				✓			

10	Download the CGM report				✓			
11	Fecal microbiota sequencing					✓		
12	Metabolite assay in serum					✓		
13	Progression events of DKD during follow-up					✓	✓	✓
14	Assessment of MACE events during follow-up					✓	✓	✓
15	Death events during follow-up		✓	✓	✓	✓	✓	✓
16	Adverse event monitoring		✓	✓	✓			
17	Deviation from plan record		✓	✓	✓	✓	✓	✓
18	Fill in CRF		✓	✓	✓	✓	✓	✓

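### The objective is an optimal GV control target, but the study content names a TIR target; for either metric, one baseline CGM recording in an observational cohort supports only a risk-associated level

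*Protocol*

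**What the plan says.** The first specific objective, in protocol section 3.1(4), is: "Evaluate the relationship between GV and prognosis in patients with DKD and determine the optimal GV control target". Section 2.1.4 describes the same purpose for the CGM data: "to investigate its relationship with prognosis and determine optimal glycemic variability control targets".

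Section 4.1.1, whose heading concerns glycemic variability and prognosis, carries this objective into the study content. Its item (2) reads: "The relationship between glycemic variability and prognosis was analyzed, and the optimal TIR control target for DKD patients was discussed".

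Section 2.1.2 puts the CGM metrics in separate classes. One class is "time in range (TIR) and its derivatives time above range (TAR) and time below range (TBR) for evaluating target-range compliance". Another is "daily glucose fluctuations measured by standard deviation (SD), coefficient of variability (CV), and mean amplitude of glycemic excursions (MAGE", closing the list of within-day fluctuation measures. The same section cites a study of 2,893 people with type 2 diabetes that compared TIR with HbA1c estimated from CGM mean glucose, "observing a good linear relationship between the two" (r = -0.91).

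The exposure is measured once. CGM is fitted at entry and worn for 14 days (sections 4.1.1 and 5.5(2)), and the schedule in section 5.6 has a single entry for "Download the CGM report", at the day-14 visit. Outcomes are then followed for 3 years (section 5.5(3)). The study is observational (sections 4.1 and 5.1).

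**The concern.** Two problems meet in one sentence of section 4.1.1.

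First, the metric changes. The objective asks for a GV target and the content section names a TIR target. The protocol itself does not treat these as synonyms: besides the classes in section 2.1.2, the note to the roadmap in section 5.2 lists TIR and GV as separate abbreviations. A cut-off on TIR therefore does not complete the objective. By the correlation the protocol cites, it would mostly sort patients by average glucose. Section 2.1.2 motivates GV as a possible risk factor in addition to HbA1c, and a TIR cut-off is poorly placed to address that.

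Second, a control target is a statement about what happens if a patient is brought to a given level. Nobody in this cohort is assigned to a level of GV or TIR. A threshold on one baseline recording describes who is at higher risk; it does not show that moving a patient across it changes the outcome.

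At stake is what the first specific objective can report: the GV target would lack a matching analysis step, and a prognostic threshold could be published as a treatment goal.

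**Working it through.** **1. The sections side by side.**

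| Section | Metric of the target | Status |
|---|---|---|
| 2.1.4 | GV | to be determined |
| 3.1(4) | GV | to be determined |
| 4.1.1(2) | TIR | discussed |

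The first half of 4.1.1(2) does analyse GV against prognosis. Only the target switches metric.

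**2. What the cited correlation implies.** Input: r = -0.91, n = 2,893 (section 2.1.2).

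- Shared variance: r² = 0.91² = 0.828, about 83%. Remainder: 1 - 0.828 = 0.172, about 17%.
- Sampling error is small. Fisher-z 95% interval: tanh(atanh(0.91) ± 1.96/√2890) = 0.904 to 0.916 in size.
- Reading this as a correlation with mean glucose assumes that estimated HbA1c is a linear function of CGM mean glucose. The protocol does not give the conversion.

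**3. How much GV information TIR could carry.** If ρ is the correlation of a GV metric with mean glucose, corr(TIR, GV) must lie within -0.91ρ ± √(1 - ρ²) × √0.172, where √0.172 = 0.415. The protocol gives no ρ, so a range is shown.

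| Assumed ρ | Possible corr(TIR, GV) |
|---|---|
| 0 | -0.41 to 0.41 |
| 0.3 | -0.67 to 0.12 |
| 0.5 | -0.81 to -0.10 |

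TIR may carry some GV information, but the protocol's figures cannot say how much.

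**4. Can a TIR effect appear with no GV effect?** Assume that only mean glucose drives risk, with a hazard ratio of 1.5 or 2.0 per SD. The approximate hazard ratio per SD of lower TIR is then 1.5^0.91 = 1.45 or 2.0^0.91 = 1.88. A clear TIR gradient is therefore compatible with no role for variability.

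**5. Is the sample size built on a target?** Section 5.4 gives 975/156 × 30 = 187.5, which reproduces. Adding 10% gives 187.5 × 1.1 = 206.25, or 187.5/0.9 = 208.3; the protocol enrols 210 in the modelling cohort. No GV or TIR level enters this calculation.

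**6. How stable would a cut-off be, even as a prognostic marker?** At the source rate (156/975 = 16% over 4.7 years), 210 patients followed for 3 years give about 210 × 0.16 × 3/4.7 = 21.4 events if events accrue in proportion to time, or 22.1 at a constant hazard. A simulation of 3,000 cohorts of 210 with about 21 events, TIR correlated -0.91 with mean glucose, risk driven by mean glucose alone, and the cut chosen by the Youden index (an assumption; the protocol names no method) gave this for the middle 95% of the chosen TIR cut:

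- odds ratio 1.5 per SD of mean glucose: 8th to 82nd percentile of TIR
- odds ratio 2.0 per SD: 12th to 73rd percentile

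**7. Target or risk level?** Section 5.5(2) allows dietary guidance, standardized regimens and dose adjustment around the recording, but none of these is tied to a GV or TIR level. There is no assigned contrast between patients held at different levels, and the schedule has no repeat CGM.

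**The case against.** The strongest reply is that section 4.1.1 does not replace GV by TIR. It analyses GV against prognosis and adds TIR as something to discuss. Sections 4.1.3 and 5.5(4) group patients by GV, and section 5.8.2 relates those groups to adverse prognosis, with regressions, including Cox, that adjust for baseline glucose among other factors. All of this stands. A reader might infer from the switch to TIR that the study can give no answer on GV at all; the documents do not support that. A GV–prognosis association can be estimated. What lacks a matching step is the GV target.

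The correlation also has limits. It comes from general type 2 diabetes, not DKD, and leaves 17% of TIR variance unexplained. The matching reference title states that glycemic variability modifies the relation between TIR and estimated HbA1c. So TIR should not be described as free of GV information. That leaves it a different metric from the one in the objective.

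A reader might also turn r = -0.91 into a precision penalty for a TIR model adjusted for baseline glucose. The documents do not support this: the baseline glucose covariate is not defined and could be the fasting value in section 5.5(1) or the laboratory glucose in section 5.6. Nor is a single baseline exposure a fault in itself, since it is ordinary cohort design; the shortness of 14 days against 3 years measures no bias. The limit concerns only what may be called a target.

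Finally, section 5.4 calls the study exploratory, and the choice of metric for a model may be left to a statistical analysis plan. Neither point removes a contradiction between the stated objective and the content meant to meet it.

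**Conclusion.** The concern holds in a limited form. The protocol sets a GV-target objective in two sections and names a TIR target in the section that implements it, while treating the two as different kinds of metric. On its own cited figure about 83% of the variance of TIR is shared with HbA1c estimated from mean glucose, so a TIR cut-off would not answer the GV-target objective and would largely reflect average glucose. This rests on carrying a correlation from general type 2 diabetes over to DKD and on the linearity assumption in step 2 of the working.

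Independently of the metric, one baseline recording in an observational cohort supports a level associated with risk, not a control target. That conclusion rests on the design alone and needs none of the numerical assumptions. The expected 21 to 22 events, if the source rate applies, are a further reason to present any such level as exploratory.

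**What to change.** Reconcile sections 2.1.4, 3.1(4) and 4.1.1(2):

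- Name, before outcomes are known, one fluctuation metric from the CGM report (SD, CV or MAGE) as the GV exposure. The protocol does not rank them, so the choice is the sponsor's.
- Include CGM mean glucose as an adjustment covariate in the GV–prognosis model, so that the covariate is defined and on the same recording.
- Report TIR separately, as glycemic control.
- Replace the wording about an optimal control target with: baseline GV (and TIR) level associated with risk of DKD progression, stated as exploratory and not a treatment target.

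The cost is small. The metrics come from the CGM recording already planned, with no new visits or samples. Mean glucose takes one more covariate in a model with few events, and the stated conclusion becomes more modest.

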#### 4.1.2 Characteristics of gut microbiota and serum metabolites in patients with DKD and their correlation with prognosis

(1) The fecal and blood samples were collected and analyzed by 16S rRNA sequencing, non-targeted metabolites and inflammatory factors.

(2) The biomarkers associated with poor prognosis were screened.

#### 4.1.3. Gut Microbiota and Serum Metabolites in DKD Patients with Different Blood Glucose Variability Groups and Their Correlation with Prognosis

(1) Patients with DKD were divided into high GV group and low GV group according to GV status, and the intestinal microbiota characteristics and serum metabolites characteristics of patients in different GV groups were analyzed.

(2) Based on the association between gut microbiota, serum metabolic biomarkers and prognosis, the relationship between the bacterial co-abundance group (CAG) and the functional modules of serum metabolites was further established to explore their correlation with glycemic variability and poor prognosis.

#### 4.1.4 Construction and validation of adverse event prediction model for DKD patients

(1) Based on the screening of the predictive factors related to adverse events in DKD prognosis, including glycemic variability index, related clinical indicators, intestinal flora, serum metabolites, inflammatory factors, etc., the predictive model was established by using machine learning algorithm, and the performance and stability of the model were evaluated.

(2) independent cohorts of patients with DKD were added as validation cohorts to evaluate the performance and stability of the predictive model.

### 4.2 Innovativeness

(1) Multidimensional assessment: On one hand, continuous glucose monitoring (CGM) technology is employed to dynamically track glycemic variability in diabetic kidney disease (DKD) patients, capturing detailed fluctuations in blood glucose levels. On the other hand, integrated analysis combines 16S rRNA high-throughput sequencing with serum non-targeted LC-MS to comprehensively evaluate gut microbiota composition and serum metabolite profiles, thereby elucidating their correlations with glycemic variability and disease prognosis.

(2) DESIGN OF PROSPECTIVE COHORT STUDY: A prospective cohort study was designed to enroll patients with different clinical stages of DKD and follow up for 3 years. Adverse prognostic events during follow-up were recorded in detail to ensure the continuity and integrity of the collected data, which provided a strong guarantee for the accuracy and reliability of the study results.

(3) multilevel data integration: the multilevel data, including glycemic variability, clinical indicators, gut microbiota, serum metabolites and inflammatory factors, were integrated to construct a predictive model for DKD prediction.

The risk of adverse prognostic events provides a more comprehensive and accurate tool for clinical risk assessment.

[figure not shown]

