**Principal Investigator: [name]**

**date :** **YTD**

## **I. Summary of the Research Plan**

Diabetic kidney disease (DKD), one of the most significant microvascular complications of diabetes, has become the leading cause of end-stage renal disease. Glycemic variability (GV) is considered closely associated with disease progression in these patients. Recent studies indicate that gut microbiota and their serum metabolites play crucial roles in regulating glycemic variability and disease prognosis. However, the mechanisms by which gut microbiota and their metabolites influence glycemic variability and subsequently affect disease outcomes in DKD patients remain unclear. This study aims to address three key questions: ① Characterizing gut microbiota and serum metabolites in DKD patients with varying disease stages and progression levels, while precisely evaluating the prognostic value of gut microbial markers for adverse outcomes. ② Investigating the relationship between gut microbiota, serum metabolites, and glycemic variability in DKD patients. ③ Determining whether gut microbiota and serum metabolites interfere with glycemic variability to influence disease prognosis. To address these questions, this observational prospective cohort study will enroll 270 patients with diabetic kidney disease. By integrating continuous glucose monitoring (CGM), 16S rRNA high-throughput sequencing, and serum non-targeted liquid chromatography-mass spectrometry (LC-MS), this study evaluated glycemic variability, analyzed gut microbiota and serum metabolites, and constructed and validated predictive models for poor prognosis in diabetic kidney disease (DKD) patients. The findings revealed correlations between gut microbiota, serum metabolites, and glycemic variability, elucidated their prognostic roles in DKD, and provided early identification tools for high-risk DKD patients. We aim to offer novel perspectives and strategies for DKD prognosis management, thereby improving clinical outcomes and quality of life for patients.

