In recent years, an increasing number of studies have shown that DKD is also an inflammatory reactive disease, in which inflammatory pathways play an important role and may be a key factor leading to the progressive damage of organs. In a hyperglycemic environment, inflammatory cell signaling pathways should be activated, mainly including P38 mitogen-activated protein kinase (MAPK), c-Jun N-terminal kinase (JNK), etc., which in turn activate the NF-κB-related signaling pathway. After activation, NF-κB stimulates the transcription of chemokines, adhesion factors, and pro-inflammatory cytokines, leading to inflammatory cell infiltration in renal tissue and promoting the occurrence and development of DKD [4]. In China, DKD has become the primary cause of end-stage renal disease in middle-aged and elderly patients [5]. Therefore, how to prioritize the prevention, identification, and management of DKD is particularly important. Although renal biopsy is the gold standard for diagnosing DKD, it has not been widely adopted due to its invasive and traumatic nature. Current diagnostic criteria for diabetic kidney disease(DKD) primarily rely on clinical manifestations, including the urine protein-to-creatinine ratio, estimated glomerular filtration rate(eGFR), serum creatinine levels, renal ultrasound findings, and retinopathy presence [6]. However, these indicators demonstrate limited diagnostic sensitivity and specificity for DKD, and fail to effectively assess the severity of renal impairment [7]. **Identifying novel biomarkers to identify high-risk populations with progressive DKD for early intervention could improve patient outcomes, establish dynamic and precise disease progression prediction models, and ultimately enable personalized treatment strategies.**

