#### **(5) Construction and Evaluation of Forecasting Model**

First, feature screening was performed using LASSO regression to select variables from five aspects: demographic characteristics, baseline scales, gut microbiota and non-target metabolites, and peripheral blood inflammatory biomarkers. Nine machine learning algorithms were employed to construct classification models, with performance evaluated through resampling training/verification mechanisms. The optimal model was selected via 10-fold cross-validation and performance metrics. Model performance and applicability were assessed using AUROC curves, calibration curves, Brier scores, and decision analysis plots. During training, validation, and testing phases of the optimal model, five-fold cross-validation and learning curves were used to evaluate model fit and stability. Finally, SHAP package was utilized to generate SHAP explanation plots to determine the importance and contribution of individual features.

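### Section 4.2 claims a more accurate risk tool, but the planned model evaluation has no clinical-only comparator and so cannot support that claim

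*Protocol*

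**What the plan says.** Section 4.2, in its item on multilevel data integration, says that combining all the data layers "provides a more comprehensive and accurate tool for clinical risk assessment". It names no reference tool.

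The modelling text describes one integrated predictor set. Section 3.2.1 states the aim: "Construct a prediction model by incorporating the above indicators to predict the prognosis of DKD patients". Section 4.1.4 lists the candidate predictors together, "including glycemic variability index, related clinical indicators, intestinal flora, serum metabolites, inflammatory factors, etc".

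Section 5.5(5) fixes the evaluation in some detail. After LASSO screening, "Nine machine learning algorithms were employed to construct classification models", and the best is chosen by 10-fold cross-validation. Then "Model performance and applicability were assessed using AUROC curves, calibration curves, Brier scores, and decision analysis plots". Finally, "SHAP package was utilized to generate SHAP explanation plots to determine the importance and contribution of individual features". Section 5.8.2 repeats the approach and adds an independent validation cohort, which section 5.4 sets at 60 patients beside a modelling cohort of 210.

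**The concern.** More accurate is a comparative statement, and it needs a second model or tool as the reference. The planned comparison is between algorithms that share the same predictors. It can show which algorithm does best, but not whether microbiota, metabolites or CGM measures improve on what the clinic already knows.

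Routine renal status is likely to carry much of the prediction, because the primary endpoint in section 3.1 is largely defined by eGFR. A good AUROC for the pooled model would be compatible with a large gain from the new markers, a small one, or none. At stake is whether a tool that needs 14 days of CGM, sequencing and LC-MS has been shown to be worth that over routine variables. Section 9 foresees promoting the model's clinical adoption.

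**Working it through.** **Step 1: what each planned output can show.**

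- Ranking of nine algorithms: compares learning methods on the same predictors, not predictor sets.
- AUROC, calibration, Brier score: absolute performance of the model to which they are applied.
- Decision analysis plots: net benefit against treating all or none, unless a second model is drawn on the same plot. None is named.
- SHAP: divides the prediction among features inside one fitted model. It does not measure the loss in performance if a block of features were left out.
- Validation cohort: tests whether the same model generalises. No comparator is carried into it.
- Adjusted regressions in 5.8.2 (named covariates: age, sex, disease duration, baseline glucose): test association given covariates, not gain in prediction. The list is open-ended but does not name baseline renal function.

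Sections 3.2.1, 4.1.4, 5.5(5), 5.8.2 and 9 contain no clinical-only model, nested comparison or measure of incremental value.

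**Step 2: the plan's own size.** Section 5.4 takes 156 events in 975 patients over a mean of 4.7 years and requires 30 events: 975/156 × 30 = 187.5. With 10% added: 187.5 × 1.1 = 206.25, or 187.5/0.9 = 208.3. Both agree with the stated 210 after rounding.

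**Step 3: events available for a comparison.** Follow-up is 3 years (section 5.5(3)). Assuming a constant hazard:

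- 4.7-year risk: 156/975 = 0.160
- hazard: −ln(1 − 0.160)/4.7 = 0.0371 per year
- 3-year risk: 1 − exp(−3 × 0.0371) = 0.105
- expected events: 210 × 0.105 = 22; 60 × 0.105 = 6

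These are counts of DKD progression. Section 3.2.1 names all-cause death as the model's primary outcome, and the protocol gives no rate for it.

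**Step 4: precision of a paired difference in AUROC.** The protocol gives no target AUROC, correlation or alpha, so these are assumptions: AUROC 0.70 (clinical) against 0.75 (full), correlation r between the two estimates of 0.5 to 0.9, two-sided alpha 0.05.

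Hanley–McNeil: SE² = [A(1−A) + (n₁−1)(Q₁−A²) + (n₀−1)(Q₂−A²)]/(n₁n₀), with Q₁ = A/(2−A) and Q₂ = 2A²/(1+A). For the difference, SE_d² = SE₀² + SE₁² − 2r·SE₀·SE₁. Power is Φ(0.05/SE_d − 1.96).

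Modelling cohort, n₁ = 22.1 and n₀ = 187.9: SE₀ = 0.065, SE₁ = 0.062. At r = 0.5, SE_d = 0.063; at r = 0.9, SE_d = 0.028.

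| Setting | Events | 95% CI half-width, r = 0.9 to 0.5 | Power, r = 0.5 to 0.9 |
|---|---|---|---|
| Modelling, 210 patients | 22 | 0.06 to 0.12 | 12% to 42% |
| Modelling, planned events (188 patients) | 30 | 0.05 to 0.11 | 15% to 52% |
| Validation, 60 patients | 6 | 0.11 to 0.23 | 6% to 15% |

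For a larger gain, 0.70 against 0.80, power at the rescaled event counts is 37% to 94% (modelling) and 14% to 47% (validation). The formulas ignore the optimism that comes from feature and algorithm selection.

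**The case against.** The strongest reply has three parts.

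First, this is an omission, and a separate SAP may exist that adds a comparator. Nothing in 5.5(5) forbids one. That stands as a limit: the point is not that the protocol lacks an analysis, but that it makes a comparative claim and specifies an evaluation, down to cross-validation folds and SHAP, that cannot bear on it.

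Second, the sentence is promotional text in an innovation section. The formal objective in 3.2.1 is only to build a model, and the hypotheses in 2.1.4 concern predictors and associations. This also stands, and it keeps the point moderate: no stated objective or hypothesis goes untested.

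Third, a comparison would often be inconclusive. The figures above confirm it. That is a reason to report an estimate with its interval or to soften the wording, not to leave the claim without any test.

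Three stronger readings are tempting and are not supported:

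- A reader might take the first key question in the Summary as comparative. It speaks of "precisely evaluating the prognostic value of gut microbial markers for adverse outcomes", which is prognostic value, not superiority over clinical variables.
- A reader might take section 2.1.1 as a commitment to beat clinical prognostic models. Its complaint is that "these indicators demonstrate limited diagnostic sensitivity and specificity for DKD" and that they assess severity poorly. This concerns diagnosis and severity; it motivates new markers but promises no prognostic comparison.
- A reader might infer that markers which merely mirror clinical status would rank high on SHAP, or that the study is bound to announce a better tool. Clinical and omics variables are to enter together after LASSO screening, so how markers perform alone says little about their rank in that model. The protocol sets no rule for declaring superiority.

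**Conclusion.** The concern holds in a limited form. As written, the plan cannot support a claim of greater accuracy, because every planned performance measure describes models on one pooled predictor set and none measures the gain over routine clinical variables. This follows from the text and rests on no numerical assumption.

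It is a moderate gap. It affects one sentence in section 4.2 and how the results are interpreted, not the validity of the association analyses, and it can be closed with little or no new data. No change in sample size follows from it.

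The event counts assume that the source rate applies here and is constant over time. The precision figures also rest on assumed AUROCs and correlations. Under them, a gain of 0.05 in AUROC would usually not be distinguishable from zero, least of all in the validation cohort.

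**What to change.** In section 5.5(5), before outcomes are known:

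1. Prespecify a clinical-only penalised model from baseline variables, for example age, sex, disease duration, blood pressure, baseline renal function, HbA1c and lipids. Add albuminuria if it is available from the DKD work-up; sections 5.5(1) and 5.6 do not list it among the tests, and a comparator without it may be weak.
2. Fit the full model on the same resamples, and apply both models to the validation cohort.
3. Report the paired change in AUROC, Brier score and net benefit with confidence intervals, labelled as an exploratory estimate.
4. Claim greater accuracy only if the paired change supports it. Otherwise reword section 4.2 to say that the tool integrates more data sources and that its added value is being estimated.

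The cost is one further model and a paired comparison, on variables that the CRF in section 5.5(1) largely covers. The drawback is a wide interval that may leave the question open, which the report should say plainly. Fixing the comparator in advance also prevents a weak one from being chosen later.
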